3.6.3 The Effect of Tralokinumab on Patient Reported Outcomes

ACQ-6 is a shortened version of the ACQ that assesses asthma symptoms (night-time waking, symptoms on waking, activity limitation, shortness of breath, wheezing and short-acting $\beta 2$ agonist use). ACQ-6 will be completed weekly by using an ePRO device. Questions are weighted equally and scored from 0 (totally controlled) to 6 (severely uncontrolled). The mean ACQ-6 score is computed as the mean of the responses from all 6 items in the questionnaire. Mean ACQ-6 score ≤ 0.75 indicates well-controlled asthma, scores greater than

Version 2.0

0.75 and less than 1.5 indicates partly controlled asthma, and a score \geq 1.5 indicates uncontrolled asthma (Juniper et al, 2006). Individual changes of at least 0.5 are considered to be clinically meaningful (Juniper et al, 2005).

We intend to follow the guidelines established by Juniper (Elizabeth Juniper, Asthma Control Questionnaire -- Background Administration and Analysis, 2004, QoL Technologies). In order to be more specific, the exact algorithm that will be implemented in imputation of the missing data will be specified in the SPP. The mean ACQ-6 score along with the changes from baseline will be summarized using descriptive statistics. The proportions of subjects achieving mean ACQ-6 \leq 0.75 (well-controlled), 0.75< mean ACQ-6<1.5 (partly controlled), and mean ACQ-6 of \geq 1.5 at Week 53 and Week 75 will be evaluated using Fisher's exact test.

The AQLQ(S) is a 32-item questionnaire that measures the health related quality of life experienced by asthma patients (Juniper et al, 1999). The questionnaire comprises 4 separate domains (symptoms, activity limitations, emotional function, and environmental stimuli). Subjects are asked to recall their experiences during the previous 2 weeks and to score each of the 32 questions on a 7-point scale ranging from 7 (no impairment) to 1 (severe impairment). The overall score is calculated as the mean response to all questions. The 4 individual domain scores (symptoms, activity limitations, emotional function, and environmental stimuli) are the means of the responses to the questions in each of the domains. The minimal important difference (MID) for the AQLQ(S) total and domain scores is 0.5 (Juniper et al, 1994).

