The overall and 4 domain scores from the AQLQ(S) responses along with their respective changes from baseline will be summarized using descriptive statistics by treatment group. Additionally, within each treatment group, the overall and 4 domain scores will be summarized by three categories, improvement (change in scores from baseline ≥ 0.5), no change (-0.5 \le change in score from baseline < 0.5), and worse (change in score < -0.5).

Mean ACQ-6 score over time and change from baseline in mean ACQ-6, overall AQLQ(s) score over time and change from baseline in AQLQ(s) over time will be plotted for overall and subgroups (see below) and for ITT population and PP population.

Subgroup analyses on ACQ-6 and AQLQ(s) will be conducted for the following subgroups:

- 1) Subjects with percentage of predicted FEV1 at baseline $\leq 60\%$, and $\leq 80\%$;
- 2) Subjects with baseline % FEV1 reversibility ($\geq 12\%$ and < 12%);

Version 2.0

- Subjects with FEV1 improvement at Week 5 and Week 13 (defined as percent change from baseline ≥ 10%) from tralokinumab group;
- 4) Subjects grouped by number of asthma exacerbations in the past year (2 vs > 2 but \leq 6 exacerbations);
- 5) Subjects grouped by chronic OCS use (presence vs absence);
- 6) Subjects grouped by Th2 status (Th2-high and Th2-low);
- 7) Subjects grouped by atopic asthma status (atopic vs. non-atopic);
- Subjects by serum baseline periostin level (>= median or < median; >= 25th percentile vs < 25th percentile; >= 75th percentile vs < 75th percentile);
- 9) Subjects grouped by baseline peripheral blood eosinophil count (< 150 Cells/UL vs >= 150; < 300 Cells/UL vs >= 300)

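### The AQLQ(S) response categories apply the 0.5 MID inconsistently by direction: a gain of exactly 0.5 is improvement, a loss of exactly 0.5 is no change

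*SAP*

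**What the plan says.** All of the relevant text is in SAP section 3.6.3.

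- Threshold: "The minimal important difference (MID) for the AQLQ(S) total and domain scores is 0.5". The sentence does not limit it to gains or to losses.
- Direction of the scale: each item is scored on a "7-point scale ranging from 7 (no impairment) to 1 (severe impairment", so a negative change is a deterioration.
- Score construction: "The AQLQ(S) is a 32-item questionnaire" and "The overall score is calculated as the mean response to all questions". The four domain scores are likewise means of their own items. The SAP does not say how many items each domain has.
- Top response category: "improvement (change in scores from baseline ≥ 0.5". The value +0.5 itself belongs here.
- Middle response category: "no change (-0.5 \le change in score from baseline < 0.5". This takes in −0.5 but leaves out +0.5.
- Bottom response category: "and worse (change in score < -0.5". The value −0.5 itself is left out.

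The categories are reported by treatment group in the AQLQ(S) response table, for the ITT and PP populations, at Stage 1 and Stage 2. The SAP states no test of them.

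**The concern.** The usual reading of a minimal important difference is the smallest change that matters, so a change equal to it counts. The SAP reads it that way for gains. For losses it requires the change to exceed the threshold. Two subjects who move by the same amount in opposite directions are then treated differently: one is credited with a response and the other is recorded as unchanged.

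The rule is clear and will be programmed as written. The lower bound of *no change* and the upper bound of *worse* agree with each other, so this is not a damaged inequality sign in the extracted text.

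At stake is the balance of improved against worse subjects within each arm. Any subject at exactly −0.5 leaves the *worse* count, and nothing offsets this on the other side.

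**Working it through.** The SAP states no figure that depends on this rule, so there is nothing to reproduce. The check has three steps.

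**1. Apply the rules at and near the boundary (exact fractions).**

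| Change | Category under the SAP |
|---|---|
| +16/32 = +0.5 | improvement |
| −15/32 = −0.469 | no change |
| −16/32 = −0.5 | no change |
| −17/32 = −0.531 | worse |

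The categories are exhaustive and do not overlap. The asymmetry is confined to the single value −0.5.

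**2. Can −0.5 occur?** For a mean of k whole-number items with none missing, changes lie on a grid of step 1/k. Exactly −0.5 needs an item-sum change of −k/2. For k = 32 this is −16, which is attainable. For odd k, −k/2 is not a whole number, so −0.5 cannot occur and the effect is zero.

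**3. Size on the overall score.** From the SAP: k = 32 and the cut-offs. Assumed, because the SAP does not give them: change normally distributed with mean μ and SD σ, rounded to the grid, items complete. With h = 1/(2k) = 1/64 = 0.0156:

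- P(improved) = 1 − Φ((0.5 − h − μ)/σ)
- P(worse, as written) = Φ((−0.5 − h − μ)/σ)
- P(worse, symmetric) = Φ((−0.5 + h − μ)/σ)

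At μ = 0, σ = 1:

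- improved = 1 − Φ(0.4844) = 31.4%
- worse, as written = Φ(−0.5156) = 30.3%
- worse, symmetric = Φ(−0.4844) = 31.4%
- difference = 1.1 percentage points

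Over a range of assumptions:

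| μ | σ | Worse, as written | Worse, symmetric | Difference (points) |
|---|---|---|---|---|
| 0 | 0.8 | 25.96% | 27.24% | 1.28 |
| 0 | 1.0 | 30.31% | 31.41% | 1.10 |
| 0 | 1.2 | 33.37% | 34.32% | 0.95 |
| 0.5 | 0.8 | 10.21% | 10.93% | 0.71 |
| 0.5 | 1.0 | 15.49% | 16.25% | 0.76 |
| 0.5 | 1.2 | 19.87% | 20.60% | 0.73 |

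Differences are taken before rounding. The range is 0.7 to 1.3 points. With the 130 subjects planned per tralokinumab arm (SAP section 2.1), this is 130 × 0.007 = 0.9 to 130 × 0.013 = 1.7 subjects.

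**Domains.** The same calculation over the same means and SDs, for purely illustrative item counts, gives about 2 to 3 points at k = 12, 3 to 5 at k = 8, 6 to 10 at k = 4, and 0 at k = 5 or 11. The SAP supports none of these counts, so they show only how strongly the answer depends on k.

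**The case against.** **It is a convention, not a contradiction.** For the AQLQ(S) the SAP says only what the MID is. It does not say that a change of exactly that size must count, or that the rule must be symmetric. The inclusive wording, "Individual changes of at least 0.5 are considered to be clinically meaningful", concerns the ACQ-6. Every subject falls in exactly one category. This stands to the extent that *contradiction* is too strong a word. An unexplained difference in how one threshold is applied to gains and losses remains.

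**A reader might infer a bias toward tralokinumab.** The SAP does not support that. The same rule applies to all arms, and the comparison of interest is tralokinumab against placebo. With an assumed placebo mean of 0, active mean of 0.5 and SD 1, the between-arm difference in *worse* on the overall score is 30.31 − 15.49 = 14.8 points as written and 31.41 − 16.25 = 15.2 points under symmetric cut-offs. In that example the written rule slightly shrinks the apparent benefit, and improvement rates do not change.

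**A reader might treat the large figures for short domains as hidden worsening.** This fails for two reasons. First, the item counts are outside the SAP. Second, much of the gap comes from the coarse grid. For an assumed 4-item domain with mean 0.6 and SD 1, *worse* is 11.0% as written and 16.5% under the symmetric rule, but the underlying normal probability is Φ(−1.1) = 13.6%. The written rule is 2.6 points below that and the symmetric rule 2.9 points above.

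**A reader might also say that the rule makes domains non-comparable.** Granularity does that separately. Under the same model at mean 0 and SD 1, improvement rates already run 31.4%, 32.3% and 35.4% for k = 32, 12 and 4, and symmetric cut-offs leave them there.

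**Deterioration is not concealed.** The scores and their changes from baseline are summarised alongside the categories. This stands and limits the consequence.

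**Conclusion.** The point holds as an inconsistency of low severity. The SAP counts a gain equal to its MID and discounts a loss of the same size, without a reason. That follows from the text alone.

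Its direction within an arm is also certain: compared with a symmetric rule, the *worse* share can fall but cannot rise. Its size on the 32-item overall score is about 1 percentage point, or 0.7 to 1.3 under the assumed means, SDs of 0.8 to 1.2 and complete items. The size for domain scores cannot be fixed from the SAP.

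Only a descriptive secondary summary is affected. The primary endpoint, alpha and power do not depend on it, and no between-arm advantage for tralokinumab is shown.

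**What to change.** In SAP section 3.6.3, for the overall score and all four domain scores:

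- *improvement*: change ≥ 0.5 (unchanged)
- *no change*: −0.5 < change < 0.5
- *worse*: change ≤ −0.5

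If the difference by direction is intended, the reason should be stated there instead.

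The cost is two inequality signs in the SAP and the matching lines of the table program. The reported *worse* share may rise slightly. The change should be made before anyone sees unblinded AQLQ(S) results, since a later change could look data-driven. It will not make response rates comparable between domains with different item counts, and should not be presented as doing so.

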3.6.4 The Pharmacokinetics (PK) and Immunogenicity of Tralokinumab

The PK and IM data of CAT-354 will be evaluated. Individual CAT-354 serum concentrations will be tabulated by treatment group with descriptive statistics. The BLQ observations will be changed to zero for mean concentration calculation. However if the calculated mean is less than the assay LLOQ, the mean value will be set to BLQ according to MedImmune SOP. Missing PK observations will be excluded from the mean calculation and PK data analysis. Anti-drug antibodies (ADA) will be assessed at Week 1, Week 37, Week 59, and Week 75. All valid assay results from subjects who receive any study drug will be included in ADA summaries. All subjects with titer information will be shown in the data listing. A summary of the actual ADA titers by treatment group and visit will also be provided. Study discontinuation blood samples will be summarized at the closest nominal time point that does not already have a value. The association of ADA titers with AEs, PK, and exacerbation rate and other clinical measures will be evaluated.

The PK data will be analyzed and reported separately by MedImmune Global PK-PD & Bioanalysis group.

Summary	Population	Analysis
Summary of CAT-354 Serum Concentration	РК	Stage 1; Stage 2
Summary of Subjects with Anti-CAT-354 Antibody	РК	Stage 1; Stage 2

3.7 Summaries to Support the Exploratory Objectives

The exploratory objectives of this study are:

 To evaluate the effect of tralokinumab on the healthcare resource utilization and productivity using the work productivity and activity impairment (WPAI)-asthma. These data will be reported in the clinical study report.

- 2) To explore the effect of tralokinumab on airway wall thickening using high-resolution computed tomography (HRCT; selected sites only). This is optional for subjects and these data will be reported separately from the clinical study report.
- 3) To explore the relationship between the clinical response to tralokinumab and the presence of peripheral biomarkers detected in blood that may be associated with upregulation of IL-13. Biomarkers will include mRNA and serum proteins. These data will be reported separately from the clinical study report.
- 4) To collect and store deoxyribonucleic acid (DNA) for future exploratory research into genes/genetic variation that may influence clinical response to tralokinumab. This is optional for subjects and these data will be reported separately from the clinical study report.

Healthcare resource utilization will be evaluated by the number and proportion of subjects who were hospitalized due to asthma as recorded on the patient ediary. In addition, descriptive statistics will be provided for number of phone calls with healthcare providers, number of physician office visits, and number of urgent care or emergency department visit.

The WPAI-Asthma is a 6-item questionnaire that assesses productivity and activity impairment over the previous week. There are a maximum of six questions and a minimum of two questions that will be completed by subjects:

- 1 =currently employment status
- 2 = hours missed due to health problems
- 3 = hours missed other reasons
- 4 = hours actually worked
- 5 = degree health affected productivity while working
- 6 = degree health affected regular activities

If the answer to question 1 is yes, currently employed, then the subject should complete all 6 questions. If the answer to question 1 is no, not currently employed, then the subject should only complete questions 1 and 6.

The WPAI-Asthma provides employment status as well as four types of scores: absenteeism (work time missed), presenteeism (impairment at work / reduced on-the-job effectiveness), work productivity loss (overall work impairment / absenteeism plus presenteeism), and activity impairment. WPAI-Asthma outcomes are expressed as impairment percentages, with higher numbers indicating greater impairment and less productivity.

Employment status, Question 1, should be summarized as Yes - continuous, Yes – not continuous (Yes response to some weeks during the study), and No for each treatment group and representing the data between Weeks 3-53.

Version 2.0

Questions 2-4 should be summarized cumulatively between weeks 3-53 for each treatment group and stratified by employment status. Questions 5-6 should be summarized as the average between weeks 3-53 for each treatment group for all subjects and stratified by employment status.

The following calculations should be used to create the outcomes of interest:

Absenteeism = Q2/(Q2+Q4)Presenteeism = Q5/10Work Productivity Loss = Q2/(Q2+Q4)+[(1-Q2/(Q2+Q4))x(Q5/10)]Activity Impairment = Q6/10

The effect of tralokinumab on airway wall thickening using high-resolution computed tomography will be analyzed separately and a separate statistical analysis plan will be prepared.

For serum proteins, change from baseline and percentage change from baseline will be summarized by treatment group and by baseline periostin level (high vs low, in which high is defined as \geq median value and low defined as < median value). For mRNA, we will compare gene expression profiles between responders and non-responders to tralokinumab using multivariate approaches including clustering.

Total IgE measurements, changes from baseline in total IgE, and percent changes from baseline in total IgE will be summarized with descriptive statistics (N, mean, median, standard deviation, minimum and maximum) at each collection time point.

Intra-patient variability for serum periostin will be evaluated during the run-in period (between Week -2 and Week 1 visits). Serum periostin over time, change from baseline, and percent change from baseline will be summarized by treatment group.

For presentation, percent change from baseline in total IgE and periostin over time by treatment group will be plotted for both ITT population and PP population.

Summary	Population	Analysis
Summary of Health Resource Utilization Data	ITT	Stage 1
Summary of Health Resource Utilization Data	РР	Stage 1
Summary of WPAI-Asthma Data	ITT	Stage 1
Summary of WPAI-Asthma Data	РР	Stage 1

MedImmune

Tralokinumab

Version 2.0

		T1
Summary of Periostin Results	ITT	Stage 1; Stage 2
Change from Baseline in Periostin Results	ITT	Stage 1; Stage 2
Percent Change from Baseline in Periostin Results	ITT	Stage 1; Stage 2
Summary of Periostin Results	PP	Stage 1; Stage 2
Change from Baseline in Periostin Results	PP	Stage 1; Stage 2
Percent Change from Baseline in Periostin Results	PP	Stage 1; Stage 2
Summary of Total IgE Results	ITT	Stage 1; Stage 2
Change from Baseline in Total IgE Results	ITT	Stage 1; Stage 2
Percent Change from Baseline in Total IgE Results	ITT	Stage 1; Stage 2
Summary of Total IgE Results	PP	Stage 1; Stage 2
Change from Baseline in Total IgE Results	PP	Stage 1; Stage 2
Percent Change from Baseline in Total IgE Results	PP	Stage 1; Stage 2
Intra-patient Variability for Serum Periostin During the Run-in Period		Stage 1

4 Missing Data

Missing data will not be imputed unless otherwise specified.

5 General Statistical Conventions

- Laboratory data reported as ND (not done) will be counted as missing when calculating summary statistics.
- In general, all calculations will be performed prior to rounding.
- All percentages will be formatted as (xx.x%) with the exception of 100% which will be displayed as (100%). For 100% and percentages less than 10, a space will be included between the "(" and the first digit, for example, (6.3%) rather than (6.3%). For 0%, the percentage will be displayed as (0.0%).

Version 2.0

- P-values will be rounded to three decimal digits. P-values that are less than 0.001 will be reported as "< 0.001" on the tables.
- For analyses of pre-dose laboratory data, if the time of the pre-dose laboratory collection actually occurs after dosing, the data will be excluded from analyses.
- If N = 1, then the standard deviation and/or standard error should be displayed as "NA". If N= 0, then all summary statistics (other than N) will be displayed as "NA".

6 References

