The summary of baseline disease characteristics will include descriptive statistics for asthma history, chronic OCS use (presence versus absence), whole blood eosinophil count, atopic asthma status (atopic vs. non-atopic) (Atopy is defined by the presence of elevated IgE specific to any one common aeroallergen on the region-specific ImmunoCap panel tested at baseline), Th2 status identified by serum total IgE and blood eosinophils (Th2-high: IgE >100 IU/mL and blood eosinophils $\geq 0.14 \times 10^{9}$ /L) (Corren et al., 2011), serum periostin level, spirometry [pre- and post-bronchodilator FEV₁ and FEV₁ % predicted, FEV₁ reversibility, forced expiratory volume in 6 seconds (FEV₆) and FEV₆ % predicted, FVC, FVC % predicted, FEV1/FVC ratio and inspiratory capacity (IC)], and patient reported outcomes [Asthma Control Questionnaire (6-item version; ACQ-6) score, Asthma Quality of Life Questionnaire Standardized Version (AQLQ(S)), Assessing Symptoms of Moderate-to-severe Asthma (ASMA) Diary, WPAI-Asthma, and EQ-5D] by treatment group.

Prior and concomitant medications will be coded using the latest available version of AstraZeneca Drug Dictionary (AZ DD). All prior and concomitant medications (including those for Asthma indication) will be presented in a data listing.

The compliance with fluticasone/salmeterol maintenance therapy categorized as subjects with \geq 80% self-reported compliance rate and subjects with < 80% self-reported compliance rate as well as the number and percent of subjects who change their background asthma controller medications post randomization to Week 53 (Stage 1 analysis) and between week 53 and end of study (Stage 2 analysis) will be summarized by treatment group.

Summary	Population	Analysis
Study Populations for Evaluation		Stage 1
Number of Subjects Randomized by Site	ITT	Stage 1
Status of Randomized Subjects at End of Study	ITT	Stage 2
Status of Randomized Subjects at End of Treatment	ITT	Stage 1
Demographics	ITT	Stage 1
Baseline Disease Characteristics	ITT	Stage 1
Summary of Medical History	ITT	Stage 1
Summary of Asthma History	ITT	Stage 1

Compliance with Fluticasone / Salmeterol Maintenance Therapy	ITT	Stage 1
Number of Subjects with Change of Background Asthma Controller Medications Post Randomization	ITT	Stage 1 / Stage 2

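### SAP 3.7 summarises WPAI work hours (Q2-4) only within employment strata observed after randomisation, so arm differences within strata can be distorted

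*SAP*

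**What the plan says.** Section 3.7 puts WPAI-Asthma under the exploratory objectives and states no test or model for it.

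- **Employment status (Q1)** has three levels: continuous, then "not continuous (Yes response to some weeks during the study), and No". It is shown "for each treatment group and representing the data between Weeks 3-53".
- **Hours items (Q2-4):** "Questions 2-4 should be summarized cumulatively between weeks 3-53 for each treatment group and stratified by employment status".
- **Impairment items (Q5-6):** "Questions 5-6 should be summarized as the average between weeks 3-53 for each treatment group for all subjects and stratified by employment status".
- **Skip rule:** "If the answer to question 1 is no, not currently employed, then the subject should only complete questions 1 and 6".
- **Derived scores:** formulas are given for absenteeism, presenteeism, work productivity loss and activity impairment. No stratification is stated for them.

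Section 3.3 lists the questionnaire among the baseline disease characteristics: "WPAI-Asthma, and EQ-5D] by treatment group". Baseline employment is not named as a stratifier anywhere.

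**The concern.** The objective is the effect of tralokinumab on productivity, and leaving a job because of asthma is itself a productivity outcome. Section 3.7 uses that outcome, observed over the same weeks as the hours, to sort subjects before the hours are summarised. If treatment changes who keeps a job, the subjects left in each stratum differ between arms for reasons other than chance, and the contrast within a stratum mixes the treatment effect with selection.

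For Q5-6 this matters less, because an all-subjects summary sits beside the stratified one. For Q2-4 no such summary is stated. Q2 and Q4 are also the inputs to absenteeism and to work productivity loss.

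**Working it through.** The SAP states no WPAI figure, so there is nothing to reproduce. The check has three steps: reading the text, an illustration of the distortion, and a check of which scale a remedy should use. All numerical inputs in steps 2 and 3 are assumed.

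**1. Reading the text.** The stratifier and the hours cover the same window, Weeks 3-53, which follows randomisation and first dose. The words for all subjects appear for Q5-6 and not for Q2-4. Under the skip rule, weeks with Q1 = No carry no Q2-5 answers. So the No stratum is empty for Q2-4, and a subject's cumulated hours stop growing when employment ends.

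**2. Distortion within strata.** Assume 70% of employed subjects have milder and 30% severe work impact, with placebo absenteeism of 5% and 20%. Tralokinumab multiplies both by a ratio r. Job loss is 2% in the milder class and q in the severe class (5-40% placebo, 2-20% tralokinumab). With class share w, absenteeism a and job-loss probability q:

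- All employed: Σwa
- Continuous: Σw(1-q)a / Σw(1-q)
- Not continuous: Σwqa / Σwq

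Worked case, r = 0.8, severe-class job loss 40% against 20%:

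- All employed: placebo 0.7×5 + 0.3×20 = 9.5%; tralokinumab 0.8×9.5 = 7.6%; difference -1.90 points.
- Continuous: placebo (0.686×5 + 0.18×20)/0.866 = 8.12%; tralokinumab (0.686×4 + 0.24×16)/0.926 = 7.11%; difference -1.01.
- Not continuous: placebo (0.014×5 + 0.12×20)/0.134 = 18.43%; tralokinumab (0.014×4 + 0.06×16)/0.074 = 13.73%; difference -4.70.

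Tralokinumab minus placebo, in points of absenteeism:

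| r | Severe-class job loss, placebo / tralokinumab | All employed | Continuous | Not continuous |
|---|---|---|---|---|
| 1.0 | 5% / 5% | 0.00 | 0.00 | 0.00 |
| 1.0 | 5% / 2% | 0.00 | +0.10 | -3.26 |
| 1.0 | 40% / 20% | 0.00 | +0.77 | -1.27 |
| 0.8 | 5% / 5% | -1.90 | -1.88 | -2.55 |
| 0.8 | 5% / 2% | -1.90 | -1.80 | -5.16 |
| 0.8 | 40% / 20% | -1.90 | -1.01 | -4.70 |
| 0.6 | 5% / 2% | -3.80 | -3.70 | -7.06 |
| 0.6 | 40% / 20% | -3.80 | -2.79 | -8.14 |

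When job loss differs, shrinkage in the continuous stratum runs from (3.80-3.70)/3.80 = 3% to (1.90-1.01)/1.90 = 47%. The not-continuous stratum moves the other way. With equal job loss and r = 0.8, its -2.55 is not bias: placebo absenteeism there is (0.014×5 + 0.015×20)/0.029 = 12.76%, and 0.2×12.76 = 2.55, so the ratio is still 0.8.

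**3. Scale of the remedy.** Assume weekly answers over 51 weeks (Weeks 3 to 53). Subjects who lose their job (10% placebo, 6% tralokinumab) miss 8 h/week until they leave after 10 weeks. All others miss 2 h/week throughout. Cumulated hours are 8×10 = 80 and 2×51 = 102.

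- Raw cumulated hours by baseline employment: placebo 0.10×80 + 0.90×102 = 99.8 h; tralokinumab 0.06×80 + 0.94×102 = 100.7 h. The arm with more job loss looks better. This happens for any exit before 102/8 = 12.75 weeks.
- Hours per employed week, taken per subject and then averaged: placebo 0.10×8 + 0.90×2 = 2.60; tralokinumab 0.06×8 + 0.94×2 = 2.36. The expected direction returns.

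So replacing the stratifier while keeping raw sums would not be enough.

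**The case against.** A reader might infer that subjects who stop work disappear and that the treatment effect is hidden. The SAP does not support that. Such subjects move to a reported stratum, defined by a "Yes response to some weeks during the study", and no stratum is ranked as the main one. Employment status is itself tabulated by arm, so a shift in job loss would be visible. Q5-6 also have an all-subjects summary. An example in which the whole effect vanishes from the continuous stratum can be built by giving both arms the same hours there, but that result is then assumed, not found.

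A reader might also infer that a subject who withdraws after a few Yes weeks counts as continuous. The SAP states no rule either way.

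Two further points have force. Q1 asks about employment and Q2 about hours missed for health, so an employed subject off sick would answer Yes and stay in the continuous stratum; only actual loss of employment moves anyone. And separating continuous from interrupted employment is a reasonable descriptive choice for cumulated hours, since step 3 shows that raw sums by baseline status can mislead.

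All of this limits the size of the point and changes the remedy. It does not alter the fact that the hours items are stated only within strata formed after randomisation.

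**Conclusion.** The point holds in a limited form. For Q2-4, section 3.7 gives only summaries within an employment status observed during Weeks 3-53, so the arms within a stratum are not a randomised comparison. Distortion between arms requires that job loss differ between them, and its direction depends on the stratum. On the assumed inputs, the continuous stratum understates the difference by about 3% to 47%, and the not-continuous stratum overstates it relative to all employed subjects. With equal job loss the continuous stratum is almost unaffected. The SAP gives no job-loss or absenteeism rates, so the real size is unknown. The stronger claim, that the effect is lost, is not shown. The objective is exploratory and the summaries are descriptive, so the priority is low.

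**What to change.** In SAP section 3.7:

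- Add a summary by treatment group of Q2-4, absenteeism and work productivity loss for all subjects employed at baseline (baseline WPAI Q1). Section 3.3 indicates that this item is available.
- Express it as Q2/(Q2+Q4) or as hours per employed week answered, not as raw cumulated hours, and say that it is computed per subject before averaging.
- Show the number of employed weeks contributing in each arm, because hours stop accruing when Q1 is No.
- Keep the by-arm table of on-study employment and read it as an outcome. Label the Weeks 3-53 strata as descriptive only.

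The cost is one extra table and a few lines of SAP text, apparently with no new data. Work hours remain uncollected for weeks not employed; no choice of stratifier recovers them.

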3.2.1 Intent-to-treat (ITT) Population

The intent-to-treat (ITT) population includes all subjects who are randomized into the study. Treatment arm will be assigned according to the initial randomization, regardless of whether subjects receive any investigational product or receive an investigational product different from that to which they were randomized.

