3.2.2 Per-Protocol (PP) Population

The per protocol (PP) population includes all subjects who have no major protocol violations, complete the treatment period, and have received at least 80% of the intended doses of investigational product during the treatment period. Major protocol violations include:

- Did not fulfill major eligibility criteria (which will be defined prior to the database lock)
- Developed withdrawal criteria but continued
- Received incorrect investigational treatment/dose

Version 2.0

Treatment classification in PP Population will be on 'as-treated' basis.

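### WPAI hours (questions 2–4) are totalled over Weeks 3–53 with no denominator, so the hours tables understate both hours missed and hours worked for subjects who leave early or skip questionnaires

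*SAP*

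**What the plan says.** SAP Section 3.7 describes the WPAI-Asthma as a questionnaire that "assesses productivity and activity impairment over the previous week". Question 2 is listed as "2 = hours missed due to health problems", question 3 covers hours missed for other reasons, and question 4 covers hours worked.

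The summary rule for these three items is: "Questions 2-4 should be summarized cumulatively between weeks 3-53", by treatment group and employment status. The next sentence treats the two rating items differently: "Questions 5-6 should be summarized as the average between weeks 3-53". Set side by side, the first rule can only mean a total.

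The section then defines four scores as the outcomes of interest. Absenteeism is question 2 divided by the sum of questions 2 and 4. Work productivity loss combines that ratio with the question 5 rating. Presenteeism and activity impairment are ratings divided by 10.

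SAP Section 4 adds: "Missing data will not be imputed unless otherwise specified". Section 3.7 specifies nothing different for the WPAI: no minimum number of answered weeks, no scaling and no divisor.

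The summary table in Section 3.7 lists the WPAI data for both ITT and PP at Stage 1. On ITT, Section 3.2.1 says: "The intent-to-treat (ITT) population includes all subjects who are randomized into the study". The PP population is limited to subjects who "complete the treatment period, and have received at least 80% of the intended doses", among other conditions.

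**The concern.** Each questionnaire looks back one week. A week without a questionnaire therefore adds nothing to the sum, whatever happened at work that week. A total over Weeks 3–53 mixes two quantities: hours per week, which is of interest, and the number of weeks reported, which is not. In the ITT summary, early leavers enter with truncated totals beside subjects followed to Week 53.

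The SAP adjusts for unequal observation elsewhere. The crude exacerbation rate in Section 3.5 is divided by person follow-up, and the model carries log days as an offset. Rescue medication use in the ASMA diary (Section 3.6.3) is a daily average with a minimum number of records per week. The WPAI hours have neither safeguard.

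At stake is the readability of the hours tables. These data go into the clinical study report, and hours of work missed is an easy figure to quote. If dropout or completion differs between arms, part or all of a difference in total hours could be an artefact of reporting.

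**Working it through.** The SAP gives no figure for the WPAI summaries, so there is nothing to reproduce. The check is direct arithmetic.

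**Inputs from the SAP:** totals for questions 2–4 over Weeks 3–53, one-week recall, no imputation, ITT including early leavers.

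**Assumptions (not in the SAP):** 2 hours missed per week out of a 40-hour week; 51 questionnaires if weekly or 26 if two-weekly; the dropout and completion rates below.

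**Step 1: one subject.** Total = hours per week × weeks answered. Absenteeism = question 2 / (question 2 + question 4).

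| Weeks answered (of 51) | Total hours missed | Shortfall | Hours per answered week | Absenteeism |
|---|---|---|---|---|
| 51 | 102 | 0% | 2.0 | 5% |
| 46 | 92 | 10% | 2.0 | 5% |
| 38 | 76 | 25% | 2.0 | 5% |
| 26 | 52 | 49% | 2.0 | 5% |
| 13 | 26 | 75% | 2.0 | 5% |

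With 26 two-weekly questionnaires, 23 answered gives a shortfall of 12% and 13 answered gives 50%. Hours worked shrink by the same proportion: 38 × 51 = 1,938 hours fall to 38 × 26 = 988. That is why absenteeism does not move: 102/(102 + 1,938) = 52/(52 + 988) = 5%.

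**Step 2: two arms with the same true hours per week.** With uniform dropout times, the expected fraction of weeks contributed is 1 − dropout/2. With skipped questionnaires, it is the completion rate.

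- Dropout 10% versus 15%: 0.95/0.925 = 1.027
- Dropout 10% versus 20%: 0.95/0.90 = 1.056
- Completion 90% versus 80%: 0.90/0.80 = 1.125

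The true ratio is 1 in each case. In hours, at 2 per week over 51 weeks, 10% dropout gives a mean total of 102 × 0.95 = 96.9 and 20% dropout gives 102 × 0.90 = 91.8.

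**Step 3: when leavers are worse off.** Suppose leavers miss 4 hours per week and leave a quarter of the way through, while the others miss 2.

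- Dropout 10%: total = 51 × (2 × 0.9 + 4 × 0.1 × 0.25) = 96.9; per answered week = 96.9/(51 × 0.925) = 2.05
- Dropout 30%: total = 51 × (2 × 0.7 + 4 × 0.3 × 0.25) = 86.7; per answered week = 86.7/(51 × 0.775) = 2.19

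The total falls while the hours missed per answered week rise, so the totals can rank the arms the wrong way round.

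**The case against.** A reader might infer that the totals bias the productivity comparison which the exploratory objective calls for. The SAP does not support that. Section 3.7 names four derived scores as its outcomes of interest, and none of them scales with the number of weeks answered. Informative dropout can still affect them, but it can equally affect the hours per answered week proposed here.

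A reader might also infer that missing weeks simply make an arm look as if it lost less work. That holds only for questions 2 and 3. Question 4 shrinks as well, which makes the same arm look as if it worked less.

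Other objections carry part of their weight:

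- Hours are additive and ratings are not, so treating questions 2–4 and 5–6 differently is no inconsistency in itself. This stands. The defect is the missing divisor.
- The PP summary removes most of the dropout effect. It does not deal with skipped questionnaires, and the ITT table remains.
- Stratifying by employment status handles some variation in eligible weeks. But on a plain reading, a leaver employed at every answered questionnaire joins the continuously employed stratum beside subjects who answered to Week 53.
- The programming plan mentioned in Section 1 is not shown and might report weeks answered. The SAP itself nonetheless prescribes the total.
- The SAP gives no dropout or completion rate and no reason to expect a difference between blinded arms. With equal rates the between-arm ratio is undisturbed, although every arm's total is still too low as a figure for Weeks 3–53.

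**Conclusion.** The point holds for the raw hours summaries of questions 2–4 and for nothing wider. As written, the totals fall in proportion to unanswered weeks, for hours missed and hours worked alike, and the ITT tables are not comparable between arms that differ in dropout or completion.

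The ratio of totals is off by about 3% to 6% for a dropout difference of 5 to 10 points with uniform dropout times, and by 12.5% for 80% versus 90% completion. These sizes rest wholly on assumed rates and on equal true hours per week. The 51-week figures also assume weekly administration, because the SAP states no WPAI interval.

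The affected tables are exploratory and descriptive, with no test attached. The primary analysis is untouched. This is a minor correction, worth making because it costs almost nothing.

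**What to change.** In SAP Section 3.7, replace the cumulative rule for questions 2–4 with hours per completed questionnaire while employed: total hours divided by the number of questionnaires completed while employed. State whether the division is made per subject or pooled over the group. Report the number of completed questionnaires by treatment group beside the hours. If a figure for the full period is wanted, multiply by the scheduled number of questionnaires, not by an assumed 51. The four derived scores need no change.

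The cost is a few words in the SAP, one derived variable and one extra row in the table. No new data are needed.
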